11.4 Recording of Data

An eCRF is required and must be completed for each subject by qualified and authorized personnel. All data on the eCRF must reflect the corresponding source document, except when a section of the eCRF itself is used as the source document. Any correction to entries made on the eCRF must be documented in a valid audit trail where the correction is dated, the individual making the correction is identified, the reason for the change is stated, and the original data are not obscured. Only data required by the protocol for the purposes of the study should be collected.

The investigator must sign each eCRF. The investigator will report the eCRFs to the sponsor and retain a copy of the eCRFs.

11.5 Identification of Source Data

All data to be recorded on the eCRF must reflect the corresponding source documents.

11.6 Retention of Records

The circumstances of completion or termination of the study notwithstanding, the investigator (or if regionally required, the head of the medical institution or the designated representative) is responsible for retaining all study documents, including but not limited to the protocol, copies of eCRFs, the Investigator's Brochure, and regulatory agency registration documents (eg, Form FDA 1572, ICFs, and IRB/IEC correspondence). The site should plan to retain study documents, as directed by the sponsor, for at least 2 years after the last approval of a marketing application in an ICH region and until there are no pending or contemplated marketing applications in an ICH region or at least 3 years have elapsed since the formal discontinuation of clinical development of the investigational product.

It is requested that at the completion of the required retention period, or should the investigator retire or relocate, the investigator contact the sponsor, allowing the sponsor the option of permanently retaining the study records.

11.7 Auditing Procedures and Inspection

In addition to routine monitoring procedures, the sponsor's Clinical Quality Assurance department conducts audits of clinical research activities in accordance with the sponsor's standard operating procedures to evaluate compliance with the principles of ICH GCP and all applicable local regulations. If a government regulatory authority requests an inspection during the study or after its completion, the investigator must inform the sponsor immediately.

11.8 Handling of Study Drug

All study drug will be supplied to the principal investigator (or a designated pharmacist) by the sponsor. Drug supplies must be kept in an appropriate secure area (eg, locked cabinet) and stored according to the conditions specified on the drug labels. The investigator (or a designated pharmacist) must maintain an accurate record of the shipment and dispensing of the study drug in a drug accountability ledger, a copy of which must be given to the sponsor at the end of the study. An accurate record of the date and amount of study drug dispensed to each subject must be available for inspection at any time. The CRA will visit the site and review these documents along with all other study conduct documents at appropriate intervals once study drug has been received by the site.

All drug supplies are to be used only for this study and not for any other purpose. The investigator (or site personnel) must not destroy any drug labels or any partly used or unused drug supply before approval to do so by the sponsor. At the conclusion of the study and as appropriate during the study, the investigator (or a designated pharmacist) will return all used and unused drug containers, drug labels, and a copy of the completed drug disposition form to the sponsor's CRA (or designated contractor).

11.9 Publication of Results

All manuscripts, abstracts, or other modes of presentation arising from the results of the study must be reviewed and approved in writing by the sponsor in advance of submission pursuant to the terms and conditions set forth in the executed CTA between the sponsor/CRO and the institution/investigator. The review is aimed at protecting the sponsor's proprietary information existing either at the date of the commencement of the study or generated during the study. The detailed obligations regarding the publication of any data, material results, or other information generated or created in relation to the study shall be set out in the agreement between each investigator and the sponsor or CRO, as appropriate.

11.10 Disclosure and Confidentiality

The contents of this protocol and any amendments and results obtained during the study should be kept confidential by the investigator, the investigator's staff, and the IRB/IEC and will not be disclosed in whole or in part to others, or used for any purpose other than reviewing or performing the study, without the written consent of the sponsor. No data collected as part of this study will be used in any written work, including publications, without the written consent of the sponsor. These obligations of confidentiality and non-use shall in no way diminish such obligations as set forth in either the Confidentiality Agreement or CTA executed between the sponsor/CRO and the institution/investigator. All persons assisting in the performance of this study must be bound by the obligations of confidentiality and non-use set forth in either the Confidentiality Agreement or CTA executed between the institution/investigator and the sponsor/CRO.

11.11 Discontinuation of Study

The sponsor reserves the right to discontinue the study for medical reasons or any other reason at any time. If a study is prematurely terminated or suspended, the sponsor will promptly inform the investigators/institutions and regulatory authorities of the termination or suspension and the reason(s) for the termination or suspension. The IRB/IEC will also be informed promptly and provided the reason(s) for the termination or suspension by the sponsor or by the investigator/institution, as specified by the applicable regulatory requirement(s).

The investigator reserves the right to discontinue the study should his/her judgment so dictate. If the investigator terminates or suspends a study without prior agreement of the sponsor, the investigator should inform the institution where applicable, and the investigator/institution should promptly inform the sponsor and the IRB/IEC and provide the sponsor and the IRB/IEC with a detailed written explanation of the termination or suspension. Study records must be retained as noted above.

11.12 Subject Insurance and Indemnity

The sponsor will provide insurance for any subjects participating in the study in accordance with all applicable laws and regulations.

12 APPENDICES

Appendix 1 Sponsor's Grading for Laboratory Values

(revised per Amendment 01)

| | Grade 1 | Grade 2 | Grade 3 | Grade 4 |
|--|---|---|---|---|
| BLOOD/BONE MARROW | | | | |
| Hemoglobin (conversion from g/dL×0.6206) | Female (ULN=15.9 g/dL) <11.1 – 10.0 g/dL <111 – 100 g/L <6.9 – 6.2 mmol/L Male (ULN=17.7 g/dL) <12.6 – 10.0 g/dL <126 – 100 g/L <7.8 – 6.2 mmol/L | <10.0 – 8.0 g/dL <100 – 80 g/L <6.2 – 4.9 mmol/L | <8.0 g/dL <80 g/L <4.9 mmol/L; transfusion indicated | life-threatening consequences; urgent intervention indicated |
| Leukocytes (total white blood cell) | <3.40 – 3.0×10 ⁹ /L <3.40 10 ³ /uL – 3000/mm ³ (ULN=10.80 10 ³ /μL) | <3.0 – 2.0×10 ⁹ /L <3000 – 2000/mm ³ | <2.0 – 1.0×10 ⁹ /L <2000 – 1000/mm ³ | <1.0×10 ⁹ /L <1000/mm ³ |
| Lymphocytes | not applicable | <700 – 500/mm ³ <0.7 – 0.5×10 ⁹ /L | <500 – 200/mm ³ <0.5 – 0.2×10 ⁹ /L | <200/mm ³ <0.2×10 ⁹ /L |
| Neutrophils | not applicable | <1.4 – 1.0×10 ⁹ /L <1400 – 1000/mm ³ | <1.0 – 0.5×10 ⁹ /L <1000 – 500/mm ³ | <0.5×10 ⁹ /L <500/mm ³ |
| Platelets | <155 – 75.0×10 ⁹ /L <155 10 ³ /uL – 75,000/mm ³ (ULN=379 10 ³ /μL) | <75.0 – 50.0×10 ⁹ /L <75,000 – 50,000/mm ³ | <50.0 – 25.0×10 ⁹ /L <50,000 – 25,000/mm ³ | <25.0×10 ⁹ /L <25,000/mm ³ |
| METABOLIC/LABORATORY | | | | |
| Albumin, serum- low (hypoalbuminemia) | 2 - 59 years (ULN=5.5 g/dL) <3.5 – 3 g/dL <35 – 30 g/L 59 -69 years (LLN-ULN) <3.6 g/dL – 3 g/dL 69 -79 years (LLN-ULN) <3.5 g/dL – 3g/dL 79 -89 years (LLN-ULN) <3.5g/dL – 3g/dL | <3 – 2 g/dL <30 – 20 g/L | <2 g/dL <20 g/L | life-threatening consequences; urgent intervention indicated |
| Alkaline phosphatase | Female: 18 -19 years >101 – 3.0×101 19 -61 years ULN=107 61 -71 years ULN=112 71 -150 years ULN=108 Male 18 -19 years >127 – 3.0×127 19 -61 years ULN=102 61 -71 years ULN=103 71 -150 years ULN=105 | >3.0 – 5.0×ULN See previous column for ULN values | >5.0 – 20.0×ULN See previous column for ULN values | >20.0×ULN See previous column for ULN values |
| Alanine aminotransferase | Female: >32 – 3.0×32 | Female: >3.0 – 5.0×32 | Female: >5.0 – 20.0×32 | Female: >20.0×32 |

| | Grade 1 | Grade 2 | Grade 3 | Grade 4 |
|---|--|--|---|---|
| | Male: >44 – 3.0 x 44 | Male >3.0 – 5.0x44 | Male: >5.0 – 20.0x44 | Male: >20.0x44 |
| Aspartate aminotransferase | >40 – 3.0x40 | >3.0 – 5.0x40 | >5.0 – 20.0x40 | >20.0x40 |
| Bilirubin (hyperbilirubinemia) | >1.2 – 1.5x1.2 | >1.5 – 3.0x1.2 | >3.0 – 10.0x1.2 | >10.0x1.2 |
| Calcium, serum-low (hypocalcemia) (conversion to mmolx0.25) | <8.5 – 8.0 mg/dL <2.13 – 2.0 mmol/L | <8.0 – 7.0 mg/dL <2.0 – 1.75 mmol/L | <7.0 – 6.0 mg/dL <1.75 – 1.5 mmol/L | <6.0 mg/dL <1.5 mmol/L |
| Calcium, serum-high (hypercalcemia) | >10.6 – 11.5 mg/dL >2.65 – 2.9 mmol/L | >11.5 – 12.5 mg/dL >2.9 – 3.1 mmol/L | >12.5 – 13.5 mg/dL >3.1 – 3.4 mmol/L | >13.5 mg/dL >3.4 mmol/L |
| Cholesterol, serum-high (hypercholesterolemia) (conversion to mmol/L x0.02586) | 0 -19 years >169 – 300 mg/dL >4.37 – 7.75 mmol/L 19 -150 years >199 – 300 mg/dL >5.15 – 7.75 mmol/L | >300 – 400 mg/dL >7.75 – 10.34 mmol/L | >400 – 500 mg/dL >10.34 – 12.92 mmol/L | >500 mg/dL >12.92 mmol/L |
| Creatinine | Female >1.00 mg/dL – 1.5x1.00 Male >1.27 mg/dL – 1.5x1.27 | Female >1.5 – 3.0x1.00 Male >1.5 mg/dL – 3.0x1.27 | Female >3.0 – 6.0x1.00 Male >3.0 mg/dL – 6.0 x1.27 | Female >6.0x1.00 Male >6.0x1.27 |
| Gamma glutamyl transpeptidase | Female >60 IU/L – 3.0x60 Male >65 IU/L – 3.0x65 | Female >3.0 – 5.0x60 Male >3.0 – 5.0x65 | Female >5.0 – 20.0x60 Male >5.0 – 20.0x65 | Female >20.0x60 Male >20.0x65 |
| Glucose, serum-high (hyperglycemia) (conversion to mmol/L x0.0555) | Fasting glucose value >99 – 160 mg/dL >5.5 – 8.9 mmol/L | Fasting glucose value >160 – 250 mg/dL >8.9 – 13.9 mmol/L | >250 – 500 mg/dL; >13.9 – 27.8 mmol/L; hospitalization indicated | >500 mg/dL; >27.8 mmol/L; life-threatening consequences |
| Glucose, serum-low (hypoglycemia) | <65 – 55 mg/dL <3.6 – 3.0 mmol/L | <55 – 40 mg/dL <3.0 – 2.2 mmol/L | <40 – 30 mg/dL <2.2 – 1.7 mmol/L | <30 mg/dL <1.7 mmol/L life-threatening consequences; seizures |
| Phosphate, serum-low (hypophosphatemia) (conversion to mmol/L x0.323) | not applicable | <2.5 – 2.0 mg/dL <0.8 – 0.6 mmol/L | <2.0 – 1.0 mg/dL <0.6 – 0.3 mmol/L | <1.0 mg/dL <0.3 mmol/L life-threatening consequences |
| Potassium, serum-high (hyperkalemia) | not applicable | >5.5 – 6.0 mmol/L | >6.0 – 7.0 mmol/L hospitalization indicated | >7.0 mmol/L life-threatening consequences |
| Potassium, serum-low (hypokalemia) | <3.5 mEq/L – 3.0 mmol/L | <LLN – 3.0 mmol/L; symptomatic; intervention indicated | <3.0 – 2.5 mmol/L hospitalization indicated | <2.5 mmol/L life-threatening consequences |
| Sodium, serum-high (hypernatremia) | >144 mEq/L – 150 mmol/L | >150 – 155 mmol/L | >155 – 160 mmol/L hospitalization indicated | >160 mmol/L life-threatening consequences |
| Sodium, serum-low (hyponatremia) | <134 mEq/L – 130 mmol/L | Not applicable | <130 – 120 mmol/L | <120 mmol/L life-threatening consequences |
| Triglyceride, serum-high (hypertriglyceridemia) | 150 – 300 mg/dL 1.71 – 3.42 mmol/L | >300 – 500 mg/dL >3.42 – 5.7 mmol/L | >500 – 1000 mg/dL >5.7 – 11.4 mmol/L | >1000 mg/dL >11.4 mmol/L life-threatening consequences |

| | Grade 1 | Grade 2 | Grade 3 | Grade 4 |
|---------------------------------------|--|----------------|--|--|
| Uric acid, serum-high (hyperuricemia) | Female >7.1 – 10 mg/dL Male >8.6 – 10 mg/dL Both ≤0.59 mmol/L without physiologic consequences | Not applicable | Female >7.1 – 10 mg/dL Male >8.6 – 10 mg/dL Both ≤0.59 mmol/L without physiologic consequences | >10 mg/dL >0.59 mmol/L life-threatening consequences |

LLN = lower limit of normal, ULN = upper limit of normal.

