9.7.1.8.3 LABORATORY VALUES

Laboratory results will be summarized using International System of Units, as appropriate. For all quantitative parameters listed in [Section 9.5.1.5.3](#), the actual value and the change from baseline to each postbaseline visit and to the end of treatment (defined as the last on-treatment value) will be summarized by visit and treatment group using descriptive statistics. Qualitative parameters listed in [Section 9.5.1.5.3](#) will be summarized using frequencies (number and percentage of subjects), and changes from baseline to each postbaseline visit and to end of treatment will be reported using shift tables. Percentages will be based on the number of subjects with both nonmissing baseline and relevant postbaseline results.

Laboratory test results will be assigned a low/normal/high (LNH) classification according to whether the value was below (L), within (N), or above (H) the laboratory parameter's reference range. Within-treatment comparisons for each laboratory parameter will be based on 3-by-3 tables (shift tables) that compare the baseline LNH classification to the LNH classification at each postbaseline visit and at the end of treatment. Similar shift tables will also compare the baseline LNH classification to the LNH classification for the highest and lowest value during the treatment period.

[Appendix 1](#) (Sponsor's Grading for Laboratory Values) presents the criteria that will be used to identify subjects with treatment-emergent markedly abnormal laboratory values (TEMAVs). Except for phosphate, a TEMAV is defined as a postbaseline value with an increase from baseline to a Grade of 2 or higher. For phosphate, a TEMAV was defined as a postbaseline value with an increase from baseline to a Grade of 3 or higher. When displaying the incidence of TEMAVs, each subject may be counted once in the laboratory parameter high and in the laboratory parameter low categories, as applicable.

Lymphocyte subsets measured (including but not limited to CD4 [T helper cells], CD8 [cytotoxic T cells], CD19 [B cells], CD16/CD56 [natural killer cells] and CD14 [macrophages] and regulatory T cells) will be summarized in the same manner as other

laboratory parameters. Mean lymphocyte subsets and the mean change from baseline in lymphocyte subsets will also be displayed graphically over time by dose.

Serum IgG, IgM, and IgA will be measured and summarized in the same manner as other laboratory parameters.

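### Appendix 1 gives uric acid the same criteria for Grade 1 and Grade 3, and puts a stray unit on the male creatinine bounds, so the markedly abnormal flag for these two analytes is not uniquely defined

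*Protocol*

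**What the plan says.** Protocol section 9.7.1.8.3 makes Appendix 1 the source of the laboratory grades. Apart from phosphate, which needs Grade 3, "a TEMAV is defined as a postbaseline value with an increase from baseline to a Grade of 2 or higher".

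In the uric acid row of Appendix 1, Grade 1 covers values above 7.1 mg/dL in women and above 8.6 mg/dL in men, up to 10 mg/dL, with the qualifier "without physiologic consequences". Grade 2 is marked as not applying. Grade 3 prints the same limits and the same qualifier again. Grade 4 starts above 10 mg/dL.

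In the creatinine row, the male cells read:

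- Grade 1: "Male >1.27 mg/dL – 1.5x1.27"
- Grade 2: "Male >1.5 mg/dL – 3.0x1.27", so the lower bound is printed as "Male >1.5 mg/dL"
- Grade 3: "Male >3.0 mg/dL – 6.0 x1.27"
- Grade 4: "Male >6.0x1.27"

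The matching female Grade 2 cell has no unit on its lower bound: "Female >1.5 – 3.0x1.00".

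**The concern.** A grading table can drive a yes/no flag only if each value falls in one grade. In the uric acid row the two cells that share a range lie on opposite sides of the TEMAV threshold, and nothing printed tells them apart. In the male creatinine row the unit turns two lower bounds into concentrations that lie below the upper bound of the preceding grade. Two programmers could each follow the protocol and report different TEMAV counts for the same data. Safety is one of the two primary objectives (section 8.1), so these counts should be reproducible from the protocol.

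**Working it through.** All inputs are the printed limits in Appendix 1 and the TEMAV rule in section 9.7.1.8.3. Each grade is treated as an interval with lower < value ≤ upper; this convention is mine. The male upper limit of normal (ULN) for creatinine is 1.27 mg/dL. The plan states no figure on this point to reproduce.

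**Uric acid.** The intervals as printed are:

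| Grade | Women (mg/dL) | Men (mg/dL) | Qualifier | TEMAV if reached from a lower grade? |
|---|---|---|---|---|
| 1 | >7.1 to 10 | >8.6 to 10 | as quoted | no |
| 2 | not used | not used | – | – |
| 3 | >7.1 to 10 | >8.6 to 10 | identical to Grade 1 | yes |
| 4 | >10 | >10 | life-threatening | yes |

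If the Grade 1 cell is applied, the flag starts above 10 mg/dL. If the Grade 3 cell is applied, it starts above 7.1 or 8.6 mg/dL. The undetermined band is 10 − 7.1 = 2.9 mg/dL wide for women and 10 − 8.6 = 1.4 mg/dL wide for men. The flag is undetermined for a subject whose baseline is at or below the ULN and who rises into the band. A subject in the band at baseline who rises above 10 mg/dL goes to Grade 4 on either reading.

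Other rows show two ways to keep such grades apart. Low sodium also leaves Grade 2 unused, but its Grade 3 starts at 130 mmol/L, where Grade 1 ends. Low potassium shares its range between Grades 1 and 2 but adds symptoms and a need for intervention to Grade 2. The uric acid row does neither.

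**Male creatinine.** The products are 1.5 x 1.27 = 1.905, 3.0 x 1.27 = 3.81 and 6.0 x 1.27 = 7.62 mg/dL.

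| Grade | Read literally (mg/dL) | Lower bounds read as multiples of 1.27 (mg/dL) |
|---|---|---|
| 1 | >1.27 to 1.905 | >1.27 to 1.905 |
| 2 | >1.5 to 3.81 | >1.905 to 3.81 |
| 3 | >3.0 to 7.62 | >3.81 to 7.62 |
| 4 | >7.62 | >7.62 |

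- Literal reading, >1.5 to 1.905: Grades 1 and 2 both apply. This band straddles the TEMAV threshold. For example, 1.7 mg/dL is Grade 1 or Grade 2.
- Literal reading, >3.0 to 3.81: Grades 2 and 3 both apply. Either grade is a TEMAV, so the flag changes only for a subject already at Grade 2 at baseline. Otherwise only the reported grade changes.
- Multiple-of-ULN reading: no overlap.
- Female row (ULN 1.00): the steps are 1.00, 1.5, 3.0 and 6.0, with no overlap on either reading.

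**The case against.** The strongest reply concerns creatinine. Appendix 1 uses one shorthand for analytes graded by multiples of the ULN, in which the multiplier printed after the upper bound applies to both bounds. Alkaline phosphatase, ALT, AST, bilirubin, GGT and female creatinine all follow it. Read literally, ALT Grade 2 would start at 3 units, below the normal limit, and bilirubin would overlap from 1.5 to 1.5 x 1.2 = 1.8. Nobody would program the table that way, so the male creatinine bounds very probably mean multiples of 1.27. This stands as to intent. It does not clear the text, because the male cells, unlike those rows, print a concentration unit on the lower bound.

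For uric acid, a shared numeric range is not in itself an error in this table, as low potassium shows. That stands too, but there the qualifier separates the grades and here it is the same. No reading of the printed words tells Grade 1 from Grade 3. Damage in text extraction is an unlikely explanation, since the cells on either side are intact and different.

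It can also be said that the central laboratory has its own grading, and that the revision history lists creatinine among the analytes aligned to it under Amendment 01. This supplies a reference for the correction but does not repair the printed rows, and uric acid is not in that list.

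A reader might infer more than this:

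- **That the TEMAV analysis as a whole is unreliable.** Two rows of 24 are affected, and one of them has an evident intended reading.
- **That men are flagged at 1.5 / 1.27 = 1.18 x ULN against 1.5 x ULN for women, so that incidence depends on the sex mix.** This holds only on the literal reading, and the protocol gives neither a sex split nor a creatinine distribution from which to show an effect.
- **That the comparison between arms is biased.** Any one reading would be applied to all arms alike, and nothing in the protocol points to a differential effect.

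**Conclusion.** The point holds, within limits. The uric acid row cannot be applied as printed: the whole range from the ULN to 10 mg/dL is Grade 1 and Grade 3 at once, so the TEMAV flag there is undetermined. The male creatinine row has a probable stray unit in two cells, and only values above 1.5 up to 1.905 mg/dL put the flag in doubt, apart from the baseline Grade 2 exception above.

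The consequence is the descriptive TEMAV incidence for these two analytes. The change-from-baseline summaries and the low/normal/high shift tables in section 9.7.1.8.3 do not use these grades. Neither do the discontinuation criteria in section 9.3.3 or any efficacy analysis. How many subjects would be affected cannot be stated, because the protocol gives no distribution for either analyte. The conclusion assumes that the printed cells are the sponsor's text. That creatinine was meant as multiples of the ULN is an inference from the neighbouring rows.

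**What to change.** - **Uric acid:** check the Grade 1 and Grade 3 cells against the sponsor's source grading and the central laboratory's grading, and restate them so that the two grades can be told apart. The protocol does not show what the distinguishing criterion was meant to be, so the sponsor has to supply it.
- **Male creatinine:** delete the unit from the Grade 2 and Grade 3 lower bounds and write them as 1.5 x 1.27 and 3.0 x 1.27. This matches the row's own upper bounds and the other multiple-of-ULN rows. Confirm it against the central laboratory's grading.

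The cost is a correction to two rows of an appendix and a check of the TEMAV program. If TEMAV output has already been produced, these two analytes would need a rerun. Data collection does not change.

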Appendix 2 List of Permitted and Prohibited Prior/Concomitant Medications

Prohibited medications are shown in [Listing 1](#) through [Listing 5](#). Medications permitted with restrictions are listed in [Listing 6 through Listing 8](#). (revised per Amendment 04) **These may not be all-inclusive listings.** Please contact the medical monitor(s) if the investigators have any questions or concerns regarding any medication not listed that your subjects may be taking before enrollment or start during the course of the E2609-G000-202 study.

Antibiotics, analgesics, and anti-inflammatory drugs intended for short courses of treatment are permitted and do not need to follow the restrictions of [Listing 8](#) for a stable dose of 4 weeks before Baseline. If these medications may affect cognitive function but the medications are clinically indicated, then cognitive testing should not take place until at least 72 hours after the last dose of the course of treatment.

Prohibited Prior/Concomitant Medications**Listing 1 Drugs with High Risk of Torsades de Pointes or QTc Prolongation**

| Generic name | Brand name (Names shown are not exhaustive and are examples only; names may be the ® or ™) | Comments |
|---|--|---|
| Prohibited from 14 days (or 5 half-lives, whichever is longer) before Randomization until after the last treatment visit | | |
| Anti-arrhythmic/ abnormal heart rhythm | | |
| Amiodarone | Cordarone; Pacerone | Incidence in females greater than males, Torsades de Pointes risk regarded as low |
| Disopyramide | Norpace | Incidence in females greater than males |
| Dofetilide | Tikosyn | |
| Ibutilide | Corvert | Incidence in females greater than males |
| Procainamide | Pronestyl; Procan | |
| Quinidine | Cardioquin; Quinaglute | Incidence in females greater than males |
| Sotalol | Betapace | Incidence in females greater than males |
| Antihistamine/ allergic rhinitis | | |
| Astemizole | Hismanal | No longer available in United States |
| Terfenadine | Seldane | No longer available in United States |
| Anti-anginal/ heart pain | | |
| Bepridil | Vascor | Incidence in females greater than males |
| Antibiotic/ bacterial infection | | |
| Clarithromycin | Biaxin | |
| Moxifloxacin | Avelox | |
| Sparfloxacin | Zagam | |
| Listing 1 continued | | |
| Antimalarial/ malaria infection | | |
| Chloroquine | Aralen | |
| Halofantrine | Halfan | Incidence in females greater than males |
| Antipsychotic/ anti-emetic/ schizophrenia/ nausea | | |
| Chlorpromazine | Thorazine | |
| Gastrointestinal stimulant/ heartburn | | |
| Cisapride | Propulsid | |

Listing 1 Drugs with High Risk of Torsades de Pointes or QTc Prolongation

| Generic name | Brand name (Names shown are not exhaustive and are examples only; names may be the ® or ™) | Comments |
|--|--|---|
| Antinausea/ nausea | | |
| Domperidone | Motillum | Not available in the United States |
| Sedative; antinausea/ anesthesia adjunct, nausea | | |
| Droperidol | Inapsine | |
| Antibiotic; gastrointestinal stimulant/ bacterial infection; increase gastrointestinal motility | | |
| Erythromycin | Erythrocin; E.E.S. | Incidence in females greater than males |
| Antipsychotic/ schizophrenia | | |
| Haloperidol | Haldol | When given intravenously or at higher than recommended doses, risk of sudden death, QT prolongation, and torsades increases |
| Mesoridazine | Serentil | |
| Thioridazine | Mellaril | |
| Opiate agonist/ pain control, narcotic dependence | | |
| Levomethadyl | Orlaam | |
| Methadone | Methadose; Dolophine | Incidence in females greater than males |
| Anti-infective/ pneumocystis pneumonia | | |
| Pentamidine | Pentam; NebuPent | Incidence in females greater than males |
| Antipsychotic/ Tourette's tics | | |
| Pimozide | Orap | Incidence in females greater than males |
| Antilipemic/ hypercholesterolemia | | |
| Probucol | Lorelco | No longer available in United States |
| Anticancer | | |
| Arsenic trioxide | Trisenox | Used for leukemia |
| Vandetanib | Zactima | Used for thyroid cancer |

Note: This list is not exhaustive.

QTc = Corrected QT interval.

Listing 2 Prohibited Medications Within 5 Half-lives or 60 days, Whichever is Longer, Before Randomization and Until after the Last Treatment Visit

| Generic name | Brand name (Names shown are not exhaustive and are examples only; names may be the ® or ™) |
|---|--|
| Systemic Immunosuppressants^{a,b} and Immunomodulatory therapy | |
| Azathioprine | Azasan, Imur |
| Ciclosporine | Gengraf, Neoral |
| Dexamethasone | Decadron, Dexasone, Diodex, Hexadrol, Maxidex |
| Fingolimod | Gilenya |
| Methotrexate | Trexall |
| Methylprednisolone | Medrol, Meprolone |
| Mycophenolate | CellCept, Myfortic |
| Prednisolone | Deltasone, Prednicot, Prednisone Intensol, Rayos, Sterapred, Sterapred DS |

Note: This list is not exhaustive.

- a: Topical and inhaled formulations with minimal systemic exposure need not be prohibited.
- b: During the treatment period of the study, short term (not more than 14 days) use of steroids up to the equivalent of prednisolone 40 mg OD is permitted after discussion with the Medical Monitor. Dosing with study drug should be suspended from the time steroid treatment is started. Complete blood count and lymphocyte subsets should be determined prior to starting steroid treatment and continue to be monitored weekly. Study drug may be resumed after discussion with the Medical Monitor when the following conditions are met: (1) treatment with steroids has been completed for at least 1 week; (2) total lymphocytes not <LLN; (3) no lymphocyte subsets are below the discontinuation threshold; (4) the investigator considers that the medical condition which required treatment with steroids has improved or resolved. Weekly testing of lymphocyte subset counts and CBC with differentials is required for 4 weeks following resumption of study drug administration. (revised per Amendment 04)

Listing 3 Prohibited Medications Within 6 Months Before Randomization

| Generic name | Brand name (Names shown are not exhaustive and are examples only; names may be the ® or ™) |
|---|---|
| Immunoglobulin therapy | |
| Adalimumab | Humira |
| Bevacizumab | Avastin |
| Efalizumab | Raptiva |
| Etanercept | Enbrel |
| Immune globulin IV, IVIG, IGIV | Carimune, Flebogamma, Gamimune N, Gammagard, Gamunex, Gammar-P IV, Iveegam, Octagam, Panglobulin, Vigam, Polygam S/D, Privigen, Sandoglobulin, Venoglobulin-S |
| Infliximab | Remicade |
| Omalizumab | Xolair |
| Ranibizumab | Lucentis |
| Other monoclonal antibodies not listed here | |

Note: This list is not exhaustive.

Listing 4 Prohibited Live Vaccines Within 3 Months Before Randomization Until after the Last Treatment Visit (this does not apply to non-live/inactivated vaccines)

| Bacterial vaccines | Viral vaccines |
|---|---|
| Bacillus Calmette-Guérin vaccine against tuberculosis | Measles vaccination |
| Cholera vaccination (oral) | Rubella vaccination |
| | Oral polio vaccination (Sabin) |
| | Yellow fever vaccination |
| | Varicella (chickenpox) vaccination |
| | Rotavirus vaccination |
| | Japanese encephalitis vaccination |
| | Live attenuated influenza vaccine (FluMist, Fluenz) |
| Typhoid vaccination (oral) | Mumps vaccination |

Note: This list is not exhaustive

Listing 5 Strong CYP3A4 Inhibitors Prohibited Within 5 Half-Lives or 14 Days (Whichever Is Longer) Before Randomization Until After the Last Treatment Visit

| Generic name | Brand name(s) |
|----------------|--|
| boceprevir | Victrelis |
| clarithromycin | Clarithromycin, clarithromycin extended release, Prevpac |
| cobicistat | Tybost, Stribild, |
| conivaptan | Vaprisol |
| danoprevir | |
| elvitegravir | Vitekta, Stribild |
| indinavir | Crixivan |
| itraconazole | Sporanoz, Onmel |
| ketoconazole | Xolegel, Nizoral, Ketodan |
| lopinavir | Kaletra |
| nefazodone | Serzone |
| nelfinavir | Viracept |
| posaconazole | Noxafil |
| ritonavir | Norvir, Kaletra |
| saquinavir | Invirase, Fortovase |
| telaprevir | Incivek |
| telithromycin | Ketek |
| tipranavir | Aptivus |
| troleandomycin | Triocetin |
| voriconazole | Vfend, Voriconazole |

Note: This list is not exhaustive

Permitted Prior/Concomitant Medications

Listing 6 Medications Which Need To Be on a Stable Dose for 12 Weeks Before the Baseline Cognitive Assessments at Visit 2 and Remain on the Same Stable Dose from Baseline to Final Follow-Up Visit

| Generic name | Brand name (Names shown are not exhaustive and are examples only; names may be the [®] or [™]) |
|----------------------------|---|
| Cognitive Enhancers | |
| Donepezil | Aricept |
| Galantamine | Reminyl |
| Memantine | Namenda |
| Rivastigmine | Exelon |

Note: This list is not exhaustive.

Listing 7 Permitted Medications Used on PRN Basis Which are Not to be Used Within 72 Hours before Cognitive Testing

| Generic name | Brand name (Names shown are not exhaustive and are examples only; names may be the ® or ™) |
|---|---|
| Opiates | |
| Morphine | Astramorph PF, Avinza, Depo Dur, Duramorph, Infumorph, Kadian, MS Contin, MSIR, Oramorph SR, RMS, Roxanol |
| Opiate Agonists | |
| Codeine | Codeine |
| Fentanyl | Actiq, Duragesic, Fentora, Onsolis, Sublimaze |
| Meperidine | Demerol, Meperitab |
| Oxycodone | Dazidox, Endocodone, Eth-OxyDose, OxyContin, OxyFast, OxyIR, Percolone, Roxicodone, Roxicodone Intensol |
| Other opioids or opioid agonists which are used on PRN basis | |
| Benzodiazepines and sedatives | |
| Alprazolam | Alprazolam Intensol, Niravam, Xanax |
| Amitriptyline | (various) |
| Chlordiazepoxide | H-Tran, Librium |
| Clonazepam | Ceberclon, Klonopin |
| Diazepam | Diastat, Dizac, Valium |
| Dothiepin | (various) |
| Estazolam | ProSom |
| Flunitrazepam | Rohypnol |
| Flurazepam | Dalmane |
| Lorazepam | Ativan |
| Midazolam | Versed |
| Olanzapine | Zyprexa |
| Promethazine | Phenergan; others |
| Ramelteon | Rozerem |
| Risperidone | Risperdal |
| Temazepam | Restoril |
| Triazolam | Halcion |
| Zolpidem | Ambien; others |
| Zopiclone | (various) |
| Other benzodiazepines, tricyclic antidepressants, antipsychotics and other drugs which are used on PRN basis as sedatives | |

Note: This list is not exhaustive

**Listing 7 Permitted Medications Used on PRN Basis Which are Not to be Used
Within 72 Hours before Cognitive Testing**

| Generic name | Brand name (Names shown are not exhaustive and are examples only; names may be the [®] or [™]) |
|--------------|--|
|--------------|--|

PRN = Pro re nata

Listing 8 Permitted Centrally Active or Psychiatric Medications

| Generic Name | Brand name (Names shown are not exhaustive and are examples only; names may be the ® or ™) |
|---|--|
| If to be used on a PRN basis see Listing 7. If to be used chronically, subjects must be on a stable dose for ≥4 weeks before Baseline. Changes in dose or initiation of new concomitant medications for chronic use (not PRN use) is permitted but if the medication affects cognitive function, do not conduct cognitive testing until the dose is stable for 4 weeks. | |
| Antidepressants | |
| Amitriptyline hydrochloride | Elavil |
| Amoxapine | Amoxapine |
| Bupropion | Aplenzin, Budeprion, Buproban, Zyban, Wellbutrin |
| Citalopram | Celexa |
| Clomipramine hydrochloride | Anafranil |
| Desipramine hydrochloride | Norpramin |
| Desvenlafaxine | Pristiq |
| Doxepin hydrochloride | Prudoxin, Silenor, Sinequan, Zonalon |
| Duloxetine | Cymbalta |
| Escitalopram | Lexapro |
| Fluoxetine | Prozac, Sarafem, Selfemra |
| Fluvoxamine | Luvox |
| Imipramine hydrochloride | Tofranil |
| Isocarboxazid | Marplan |
| Maprotiline hydrochloride | Ludiomil |
| Mirtazapine | Remeron Soltab |
| Nortriptyline hydrochloride | Aventyl, Pamelor |
| Paroxetine | Paxil, Pexeva |
| Phenelzine | Nardil |
| Protriptyline hydrochloride | Vivactil |
| Rasagiline | Azilect |
| Selegiline | EMSAM |
| Sertraline | Sertaraline, Zoloft |
| Tranlycypromine | Parnate |
| Trazodone hydrochloride | Desyrel, Oleptro |
| Trimipramine maleate | Surmontil |
| Venlafaxine hydrochloride | Effexor |

Listing 8 Permitted Centrally Active or Psychiatric Medications

| Generic Name | Brand name (Names shown are not exhaustive and are examples only; names may be the ® or ™) |
|---|--|
| Mood Stabilizers (Listing 8 continued) | |
| Carbamazepine | Carbatrol, Epitol, Equetro, Tegretol, Tegretol XR |
| Lamotrigine | Lamictal, Lamictal CD, Lamictal ODT, Lamictal XR |
| Valproic acid | Depacon, Depakene, Depakote, Depakote ER, Divalproex Sodium, Stavzor, Valproate |
| Antipsychotics | |
| Acetophenazine | Tindal |
| Aripiprazole | Abilify |
| Asenapine | Saphris |
| Olanzapine | Zyprexa |
| Chlorpromazine | Thorazine |
| Haloperidol | Haloperidol, Haldol |
| Clozapine | Clozaril, Fazaclo |
| Fluphenazine | Prolixin |
| L-Methylfolate | Deplin, L-Methylfolate Calcium |
| Loxapine | Loxitane |
| Mesoridazine | Serentil |
| Perphenazine | Trilafon |
| Quetiapine | Seroquel |
| Risperidone | Risperdal |
| Thioridazine | Mellaril |
| Thiothixene | Navane |
| Trifluoperazine | Stelazine |
| Benzodiazepines | |
| Alprazolam | Alprazolam Intensol, Niravam, Xanax |
| Chlordiazepoxide | H-Tran, Librium |
| Clonazepam | Ceberclon, Klonopin |
| Diazepam | Diastat, Dizac, Valium |
| Estazolam | ProSom |

Listing 8 Permitted Centrally Active or Psychiatric Medications

| Generic Name | Brand name (Names shown are not exhaustive and are examples only; names may be the ® or ™) |
|---------------|--|
| Flunitrazepam | Rohypnol |
| Flurazepam | Dalmane |
| Lorazepam | Ativan |
| Midazolam | Versed |
| Temazepam | Restoril |
| Triazolam | Halcion |
| Zopiclone | Imovane, Zimovane |
| Zopidem | Ambien, Ambien CR, Intermezzo, Stilnox, Stilnoct, Sublinox, Hypnogen, Zolsana |

Note: This list is not exhaustive.

PRN = Pro re nata

